17.2 Site Investigators' Assessment

The Chief Investigator is responsible for the care of the participant, or in his/her absence a delegated medical practitioner and is responsible for assessment of any event for:

• Seriousness

Assessing whether the event is serious according to the definitions given in section 17.1.

Causality

Assessing the causality of all serious adverse events/reactions in relation to the trial treatment according to the definition given. If the SAE is assessed as having a reasonable causal relationship, then it is defined as a SAR.

• Expectedness

Assessing the expectedness of all SAEs according to the definition given. If the SAE is unexpected, then it is a SUSAR.

• Severity

Assessing the severity of the event according to the following terms and assessments. The intensity of an event should not be confused with the term "serious" which is a regulatory definition based on patient/event outcome criteria.

- o Mild: Some discomfort noted but without disruption of daily life
- o Moderate: Discomfort enough to affect/reduce normal activity
- Severe: Complete inability to perform daily activities and lead a normal life

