13.6 Unblinding

The code breaks for the trial will be held in the research office of the renal department and are the responsibility of the CI [name].

If a patient has a significant adverse reaction or a SUSAR then they should stop the study medication and be managed by their clinical team as if the patient was on the active drug. Further advice should be sought from the CI as necessary.

In the event a code is required to be broken a request for unblinding will be made by the Investigator or treating health care professional.

If the person requiring the unblinding is not the CI or their team then the healthcare professional will notify the Investigator team that an unblinding is required for a trial subject which will then occur.

In emergency situations, the responsibility to break the unblinding treatment code resides solely with the CI and will not be delayed in any way. The CI may delegate this duty to the sub-I or senior renal research nurse if there would otherwise be unreasonable delay in unblinding.

On receipt of the treatment allocation details the CI or treating health care professional will continue to deal with the participant's medical emergency as appropriate.

The CI must document the breaking of the code and the reasons for doing so on the CRF/data collection tool, in the site file and medical notes. The CI will ensure it is also documented in the final study report and/or statistical report at the end of the study.

The written information will be disseminated to the Trial Steering Committee.

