17.1 General Definitions

Term	Definition
Adverse Event (AE)	Any untoward medical occurrence in a participant to whom a medicinal product has been administered, including occurrences which are not necessarily caused by, or related to, that product.
Adverse Reaction (AR)	An untoward and unintended response in a participant to an investigational medicinal product which is related to any dose administered to that participant.
	The phrase "response to an investigational medicinal product" means that a causal relationship between a trial medication and an AE is at least a reasonable possibility: i.e. the relationship cannot be ruled out.
	All cases judged by either the reporting medically qualified professional or the Sponsor as having a reasonable suspected causal relationship to the trial medication qualify as adverse reactions.
Serious Adverse Event (SAE)	 A serious adverse event is any untoward medical occurrence that: Results in death. Is life-threatening. Requires inpatient hospitalisation or prolongation of existing hospitalisation. Results in persistent or significant disability/incapacity. Consists of a congenital anomaly or birth defect.
	Other 'important medical events' may also be considered serious if they jeopardise the participant or require an intervention to prevent one of the above consequences.
	NOTE: The term "life-threatening" in the definition of "serious" refers to an event in which the participant was at risk of death at the time of the event; it does not refer to an event which hypothetically might have caused death if it were more severe.
Serious Adverse Reaction (SAR)	An adverse event that is both serious and, in the opinion of the reporting Investigator, believed with reasonable probability to be due to one of the trial treatments, based on the information provided.
Suspected Unexpected Serious Adverse Reaction (SUSAR)	 A serious adverse reaction, the nature and severity of which is not consistent with the information about the medicinal product in question set out in the Reference Safety Information (RSI): In the case of a product with a marketing authorisation, in the summary of product characteristics (SmPC) for that product. In the case of any other investigational medicinal product, in the investigator's brochure (IB) relating to the trial in question.

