17.6 Adverse events that do not require reporting

It is standard protocol to stop CMV prophylaxis within the first-year post transplant. It is also standard practice to wean some patients off prednisolone medication in the first year.

Therefore we do not consider these changes an adverse event and they will not be formally reported.

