17.8 Sponsor Medical Assessment

The CI retains overall responsibility for oversight of IMP safety profile and medical assessment of SAEs and SUSARs. The CI must review all SAEs within 48 hours of receipt. This review should encompass seriousness, relatedness and expectedness. Day 0 for all SUSARs is when the SAE/SUSAR is received by the CI and/or coordinating team and/or sponsor whichever is first.

It is expected that the CI will achieve oversight of IMP safety profile through trial committees as per section 28.0.

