APPENDIX 1: Safety Reporting Responsibilities

Sponsor: QMUL

Trial: ADOPTION

AstraZeneca Reference number:

Sponsors and AstraZeneca will exchange safety information in accordance with the requirements set out in the summary table at the end of this document.

The following information is required.

Before the trial starts:

Sponsor will provide AstraZeneca with:

- A copy of the format of the SAE report form including the AZ Reference number.
- An example of the format by which SAEs (including SUSARS) will be reported from sponsor to AZ. This should include the format of any individual reports (this may be the same form used for reporting SAEs above) and/or the format of quarterly listings if appropriate.
- The format by which site and patient ID will be presented in safety reports so that they can be entered in a consistent way on the AZ safety database.

AstraZeneca will provide the sponsor with:

- The current IB An adverse event should only be considered expected for an AstraZeneca Investigational Medicinal Product (IMP) if it is included in Section 5.4 of the IB. These will be available to access through ES²ROS – Externally Sponsored Scientific Research Operations System
- The contact information for our safety reporting: [contact]. All information that needs to be shared with AstraZeneca should be sent to Kinapse at the email address provided according to the guidelines set out in subsequent sections of this document.

During the Trial Sponsor will:

- Report unblinded Suspected Unexpected Serious Adverse Reactions (SUSARs) to AstraZeneca (via Kinapse) as individual case reports as they occur
- Report blinded listings of Serious Adverse Events (SAEs) and Suspected Serious Adverse Reactions (SSAR's) to AstraZeneca on a quarterly basis.
- Inform AstraZeneca within 24 hours of knowledge of the event of any emerging safety data or actions that the Sponsor is considering as a result of a safety signal with the IMP. This includes but is not limited to:
 - Urgent safety measures to be implemented in the study
 - Safety amendments to protocol/patient information & informed consent
 - Open reports from Independent Data Monitoring Committees (IDMCs) excluding confidential reports to IDMC and minutes of IDMC meetings
 - Interactions with Regulatory Authorities (RA's)/ Ethics Committees (EC's)
 - Inform AZ on an ongoing basis of any new safety trends or signals observed during routine safety surveillance activities

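### Section 17.2 classes any unexpected SAE as a SUSAR, whereas section 17.1 also requires a suspected causal link to trial treatment

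*Combined protocol and SAP*

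**What the plan says.** Section 17.1 sets out the definitions. An SAE is defined by seriousness alone. A SAR is a serious event that is, in the reporting investigator's opinion, "believed with reasonable probability to be due to one of the trial treatments". A SUSAR is "A serious adverse reaction, the nature and severity of which is not consistent with the information about the medicinal product in question" as set out in the reference safety information.

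Section 17.2 then lists the assessments for each event. The causality bullet says: "If the SAE is assessed as having a reasonable causal relationship, then it is defined as a SAR". The expectedness bullet asks for expectedness to be assessed for all SAEs by the definition given, and closes with: "If the SAE is unexpected, then it is a SUSAR".

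Three other places bear on how events reach that sentence or are checked after it:

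- Section 17.3 describes the reference safety information as the basis for judging whether an adverse *reaction* is expected.
- Section 17.8 requires the chief investigator to review every SAE within 48 hours: "This review should encompass seriousness, relatedness and expectedness".
- Appendix 1 states that an event "should only be considered expected for an AstraZeneca Investigational Medicinal Product (IMP) if it is included in Section 5.4 of the IB".

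**The concern.** A SUSAR has three elements in 17.1: seriousness, suspected causality and unexpectedness. The closing sentence of the expectedness bullet in 17.2 asks for only two of them. It speaks of the SAE, a term with no causal content, although the bullet just above has introduced the term SAR.

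The label has operational consequences in this protocol:

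- **Study medication.** Section 13.6 says: "If a patient has a significant adverse reaction or a SUSAR then they should stop the study medication".
- **Blinding.** Under 17.10 the sponsor is unblinded for the MHRA report, while the chief investigator stays blinded.
- **Supplier reporting.** Under 17.7 and Appendix 1 a SUSAR goes to the supplier as an unblinded individual case report. Other SAEs go in a blinded quarterly listing.

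Followed literally, 17.2 would send unrelated events down all three routes. Assessing expectedness for every SAE is not itself a fault, since it agrees with 17.8. The fault is confined to the conclusion drawn from that assessment.

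**Working it through.** The protocol gives no figure to reproduce here. The check compares two rules as logical conditions.

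**Rules**

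- 17.1: SUSAR = serious AND suspected related AND unexpected.
- 17.2, closing sentence: SUSAR = serious AND unexpected.

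**Enumeration.** Every event considered is already an SAE, so seriousness is met. Relatedness and expectedness are each taken as yes/no, giving 2 × 2 = 4 cases.

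| SAE is | SUSAR under 17.1 | SUSAR under 17.2 sentence | Agree? |
|---|---|---|---|
| Related, expected | No | No | Yes |
| Related, unexpected | Yes | Yes | Yes |
| Unrelated, expected | No | No | Yes |
| Unrelated, unexpected | No | Yes | **No** |

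The rules agree in 3 of 4 cases. The 17.2 sentence over-classifies in 1 and misses a 17.1 SUSAR in 0. These counts describe the kinds of event affected, not how often they occur.

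**Can the disputed case arise?** Two passages indicate that it can.

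- Section 17.6 removes only two routine medication changes from reporting (stopping CMV prophylaxis and weaning prednisolone): "Therefore we do not consider these changes an adverse event and they will not be formally reported". It does not filter out serious transplant complications.
- Appendix 1 makes an event expected only if it appears in Section 5.4 of the Investigator's Brochure. Any SAE not listed there is unexpected, whatever its cause.

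**Does any other text supply the missing condition?**

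- The causality bullet in 17.2 says when an SAE becomes a SAR, but the SUSAR sentence does not refer back to it.
- The reference to the definition given stands in the preceding sentence and governs how expectedness is assessed. It does not state what makes an unexpected event a SUSAR.
- Section 17.3 ties expectedness to reactions, which supports the 17.1 reading, but it does not amend the 17.2 rule.
- Section 17.8 lists relatedness among the items to review without making it a condition of SUSAR status.

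None of these closes the gap.

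**Effect per mislabelled event.** Under the Appendix 1 summary table, the supplier report changes from a line in a blinded quarterly listing to an unblinded individual report, due within one business day of the report to the regulatory authority. The provisions of 13.6 and 17.10 also apply.

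**Number of events.** This cannot be computed. The documents give no SAE rate for this trial and do not reproduce Section 5.4 of the Investigator's Brochure.

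**The case against.** The strongest reply is that this is a drafting slip and not a competing rule. The bullets in 17.2 run in sequence, so an assessor has already recorded causality on reaching expectedness. Section 17.1 is the only place where a SUSAR is defined, 17.3 directly after 17.2 speaks of whether a reaction is expected, and Appendix 1 keeps SAEs and suspected SARs apart from SUSARs. On that view SAE was written for SAR, trained staff would not be misled, and the 17.8 review would catch an error.

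Much of this stands. A slip is the likely explanation, and nothing in the documents shows an unrelated SAE actually being handled as a SUSAR. But the sentence is an operative instruction, and the scope of the preceding one (all SAEs) reinforces its literal meaning. The 17.8 review is not a separate check either: the chief investigator is responsible for the 17.2 assessment, carries out the 17.8 review, and is named in 17.10 as the sponsor's medical assessor.

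A second objection is that the four-case comparison treats relatedness as a single yes/no property, whereas 17.1 words causality differently for an adverse reaction (a relationship that cannot be ruled out, judged by the reporter or the sponsor) and for a SAR (reasonable probability in the investigator's opinion). That is fair. The counts assume that one causality judgement is carried through, and the difference between those two rows is a separate matter.

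The practical reach is also limited. Under 13.5 the sponsor staff who report SUSARs are already unblinded, and no unblinding of the patient or study team follows from the label. Patients who stop study medication under 13.8 or 15.15 stay in the other study activities, and 19.5 specifies an ITT analysis.

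**Conclusion.** The contradiction is real. A serious, unexpected event judged unrelated to trial treatment is a SUSAR under 17.2 and not under 17.1. The error runs one way: 17.2 over-classifies in one of four types of SAE and misses none, provided causality is treated as one yes/no judgement. How many events would be affected is unknown.

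The severity is minor. Endpoints, sample size and the significance level are untouched. What is exposed is the handling of individual events, namely possible avoidable stops of study medication and unblinded reports, if staff follow the sentence as written.

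**What to change.** Keep the expectedness assessment for all SAEs, which agrees with 17.8, and replace only the last sentence of the bullet in 17.2. Suggested wording:

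> An SAE that has been classed as a SAR under the causality bullet above, and that is also unexpected, is a SUSAR.

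The fourth case in the table then becomes No under both sections, and all four agree with 17.1, on the same assumption of a single causality judgement. The change does not settle the differing causality wording of the adverse reaction and SAR rows in 17.1. No change to 13.6, 17.7, 17.8 or 17.10 is proposed, and this point takes no position on the rule for stopping medication.

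The cost is one sentence in a protocol amendment, with no change to data, visits or procedures.

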17.3 Reference Safety Information

Reference Safety Information is the information used for assessing whether an adverse reaction is expected. See IB Edition 9, September 15th 2020 for further details.

Undesirable effects

Across clinical studies, AZD1656 has been well tolerated and no safety concerns have been raised. No safety signals have been identified regarding vital signs, ECG, weight, BMI and physical findings.

There have been no treatment related changes in safety laboratory variables including muscle biomarkers and liver function tests in Phase I to IIa. From the few

cases with increased liver enzymes in Phase IIb, a minor increase from AZD1656 treatments could not be excluded.

From the phase IIb published studies the following side effects occur more frequently than placebo.

See below for tables 3 and 4 taken from AZD1656 IB version 9 2020.

	Total		AZD1656 as monotherapy in D1020C00002		AZD1656 given on top of metformin in		AZD1656 given on top of insulin in D1020C00020	
Preferred Term	AZD1656 12.6-90 mg bd N=49	Placebo N=18	part AZD1656 15-45 mg bd N=15		D1020C AZD165 6 5-50 mg bd N=19	C00019 Placeb o N=8	AZD165 6 12.6- 90 mg bd N=15	Placeb o N=5
Total number of subjects with AE	40	13	11	3	16	7	13	3
Headache Blood glucose decreased	15 11	5 1	1	2	4 9	2 1	10 2	1
Pain in extremity Diarrhoea Upper respiratory tract	7 5 5	2 1	3 1 5		1		4 3	2 1
Urinary tract infection Abdominal pain upper	4 2	1	1 1				3	1
Application site reaction Catheter site pain	2 2						2	
Constipation Dizziness	2 2	3	1	1	1 1	2	1	
Ecchymosis Erythema Nausea	2 2 2	2	1 1 1		1	1	1	1
Rhinorrhoea	2	-	-		1	•	1	1

Table 3Adverse Events reported during treatment by at least 2 subjects on
either AZD1656 or placebo in the Phase IIa 28-day studies; number of
subjects and presented by preferred term

All AE reported by at least 2 subjects

Table 4

Study D1020C00009, add-on to metformin: Number (%) of subjects who had at least 1 AE in any category for Placebo, Glipizide, Open label AZD1656 and total AZD1656 cohort 1 (safety analysis set 0-6 month all patients (regardless of rescue))

AE category		Number (%) of patients ^a							
	Placebo (n=87)		Glipizide (n=93)		AZD1627 Open label dose ^b (n=71)		Total AZD1656 Cohort 1 ^c (n=272)		
Any AE	32	(36.8)	38	(40.9)	22	(31.0)	114	(41.9)	
Any AE with outcome = death	0		0		0		0		
Any SAE (including events with outcome = death)	2	(2.3)	3	(3.2)	1	(1.4)	5	(1.8)	
Any AE leading to discontinuation of treatment (DAE)	1	(1.1)	2	(3.2)	1	(1.4)	13	(4.8)	
Any other significant AE (OAE) ^d	0		0		0		0		
Mild AE	24	(27.6)	3	(3.2)	1	(1.4)	5	(1.8)	
Moderate AE	12	(13.8)	2	(3.2)	1	(1.4)	13	(4.8)	
Severe AE	2	(2.3)	0		0		0		

Special warnings and precautions for use

Nil

17.4 Notification and Reporting Adverse Events or Reactions

If the AE is not defined as SERIOUS, the AE is recorded in the CRF and the participant is followed up by the research team. The AE is documented in the participant's medical notes (where appropriate) and the CRF.

If, as part of the routine care of patients post-renal transplant, the clinical care team withhold the study medication, they must inform the Cl/research team. Members of the transplant team will be educated on the protocol and study requirements.

In addition to ensure that all AEs are gathered by the research team during the 3month treatment period in a timely manner, the research team will review the source documents (clinic letters and or clinical entries on electronic patient record) on a regular basis (maximum every month).

17.5 Notification of AEs of special interest

There are no Adverse Events of Special Interest for this trial.

17.6 Adverse events that do not require reporting

It is standard protocol to stop CMV prophylaxis within the first-year post transplant. It is also standard practice to wean some patients off prednisolone medication in the first year.

Therefore we do not consider these changes an adverse event and they will not be formally reported.

17.7 Notification and Reporting of Serious Adverse Events & SUSARs

All Serious Adverse Events (SAEs) will be recorded in the participants' notes, the CRF, the sponsor SAE form, and reported to the sponsor (Joint Research Management Office) within 24 hours of the CI or co-investigators becoming aware of the event. Nominated co-investigators (as listed in the delegation log) will sign the SAE forms in the absence of the CI.

Reporting of SUSARs

Suspected Unexpected Serious Adverse Reactions (SUSARs) that occur during the trial will be reported to the sponsor (joint management research office) within 24 hours of the CI or co-investigator becoming aware of the event. The sponsor will then report this to the MHRA.

Reporting of SAE/SUSAR to Astra Zeneca (see appendix 1: Safety Reporting Responsibilities)

Report unblinded Suspected Unexpected Serious Adverse Reactions (SUSARs) to AstraZeneca (via Kinapse) as individual case reports as they occur.

17.8 Sponsor Medical Assessment

The CI retains overall responsibility for oversight of IMP safety profile and medical assessment of SAEs and SUSARs. The CI must review all SAEs within 48 hours of receipt. This review should encompass seriousness, relatedness and expectedness. Day 0 for all SUSARs is when the SAE/SUSAR is received by the CI and/or coordinating team and/or sponsor whichever is first.

It is expected that the CI will achieve oversight of IMP safety profile through trial committees as per section 28.0.

17.9 Urgent Safety Measures

The CI may take urgent safety measures to ensure the safety and protection of the clinical trial subjects from any immediate hazard to their health and safety. The measures should be taken immediately. In this instance, approval from the

Competent Authority prior to implementing these safety measures is not required. However, it is the responsibility of the CI to attempt, where possible, to discuss the proposed measures with the Sponsor and Medical Advisor at the MHRA (via telephone) prior to implementing them if possible.

The CI has an obligation to inform both the MHRA and Research Ethics Committee **in writing within 3 days**, in the form of a substantial amendment. The sponsor (JRMO) must be sent a copy of the correspondence with regards to this matter as soon as it is sent.

17.10 Procedures for reporting blinded SUSARs

The CI as sponsor medical assessor will assess the event blinded, and will assess for active IMP and Placebo. For SUSARS the CI will remain blinded, however the sponsor will be unblinded for reporting to the MHRA.

17.11 Pregnancy

If a patient becomes pregnant whilst enrolled in the study, the study medication will be withdrawn but the patient will continue on in the study. No data is available on the effects of AZD1656 on pregnancy and lactation in humans. Results from the reprotoxicity studies in animals (fertility and embryo-foetal development) support inclusion of women of childbearing potential in clinical studies, provided that pregnancy is prevented using a reliable form of contraception. The results from the animal studies suggest that any adverse effect observed was as a result of maternal hypoglycaemia.

If a patient on the study medication becomes pregnant the CI has the responsibility to ensure that the pregnancy form is completed and sent to the sponsor within the agreed timelines. The initial report should be sent within 24 hours and follow up information submitted as and when it becomes available up to agreed follow up time after birth.

If a female patient on the study medication, or the female partner of a patient on the study medication, becomes pregnant, she will be asked to sign an additional consent form to allow data collection and monitoring during her pregnancy.

